5.4.2.2.3. Serious adverse events

An AE is considered to be an SAE if the field "Serious?" is answered "Yes" in the eCRF module 'Adverse Event', in case information on seriousness is missing, the AE is conservatively considered to be serious.

5.4.2.2.4. Adverse events leading to permanent discontinuation of study treatment

An AE is considered to be an AE leading to discontinuation if the field "Action taken with study drug" is answered "Permanently discontinued" in the eCRF module 'Adverse Event'.

5.4.2.2.5. Adverse events leading to temporary interruption of study treatment

An AE is considered to be an AE leading to discontinuation if the field "Action taken with study drug" is answered "Temporarily interrupted" in the eCRF module 'Adverse Event'.

5.4.2.2.6. Adverse events leading to hospitalization

AEs leading to hospitalization are those where the eCRF question 'Did the Adverse Event require subject hospitalization?' is recorded as 'Yes' on the Adverse Event eCRF.

5.4.2.2.7. Fatal adverse events

Fatal AEs are those with 'Fatal' reported as outcome.

5.4.2.2.8. Deaths

Death information (date of death and primary cause) is taken from the Death eCRF.

5.4.2.2.9. Post-treatment AEs and SAEs

Post-treatment (S)AEs are (S)AEs occurring after the last treatment administration + 15 days up to extension EOS.

5.4.2.2.10. Adverse events of special interest (AESI)

AESIs include the anticipated risks of treatment with study drug and events that may be related to MS comorbidities. The following safety areas are addressed by the pre-defined AESIs; detailed definition is given in Appendix 8:

- Bradyarrhythmia occurring post-first dose
- Macular edema
- Bronchoconstriction
- Severe liver injury
- Serious opportunistic infections including PML

- Skin cancer
- Non-skin malignancy
- Convulsions
- Unexpected neurological or psychiatric symptoms/signs (PRES, ADEM, atypical MS relapses)

5.4.2.2.11. Major adverse cardiovascular events (MACE)

Based on a pre-defined list of preferred terms belonging to relevant Standardized Medical Dictionary for Regulatory Activities Queries (SMQs), AEs are selected for the major adverse cardiovascular event (MACE) adjudication board evaluation. For each case sent for MACE adjudication, the board members individually assess whether the case is a myocardial infarction, a stroke, or another AE. For fatal cases, each member determines whether the death is considered of cardiovascular, non-cardiovascular, or undetermined cause. If not all individual assessments concur, the case is classified into the above listed categories based on a consensus meeting. For data analysis, each case is assigned to one of the following categories:

- cardiovascular death (if a death case is classified as cardiovascular);
- non-fatal myocardial infarction (if the case is classified as myocardial infarction but not as cardiovascular death);
- non-fatal stroke (if the case is classified as stroke but not as cardiovascular death);
- no MACE (if the case is classified as other adverse event, but not as cardiovascular death).

The onset date and treatment-emergent status of a MACE is determined by the onset date and treatment-emergent status of the corresponding AE. In case more than one AE is linked to the same MACE case, the earliest treatment-emergent AE onset date determines the MACE onset date; if none of the linked AEs are considered treatment-emergent, the earliest AE onset date determines the MACE onset date. This may lead to cardiovascular death MACE with an onset date prior to the date of death.

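### The adjudicated outcome 'undetermined cause of death' has no MACE analysis category: it becomes no MACE when the event is another AE, and a non-fatal event when it is an infarction or stroke

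*SAP*

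**What the plan says.** Section 5.4.2.2.11 describes two adjudication questions.

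- Event type is asked of every case: "the board members individually assess whether the case is a myocardial infarction, a stroke, or another AE".
- Cause of death is asked only where the subject died: "each member determines whether the death is considered of cardiovascular, non-cardiovascular, or undetermined cause". Disagreements go to a consensus meeting.

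The section then says "For data analysis, each case is assigned to one of the following categories". There are four, and in substance they work as follows.

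- A case counts as a cardiovascular death only if the board attributes the death to a cardiovascular cause.
- An infarction without that attribution has its own rule: "non-fatal myocardial infarction (if the case is classified as myocardial infarction but not as cardiovascular death".
- Strokes are treated in the same way as infarctions.
- What is left over goes to the last category, worded as "no MACE (if the case is classified as other adverse event, but not as cardiovascular death".

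Section 5.4.2.3.6 tabulates subjects with any treatment-emergent MACE and with each of the three MACE subcategories, by core treatment group, for the Combined and Extension Analysis Periods. It adds a listing of MACE. It mentions no row, footnote or sensitivity count for deaths of undetermined cause.

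**The concern.** The board records three causes of death, but the analysis distinguishes only cardiovascular from everything else. A verdict that the cause could not be determined thus has the same effect as a verdict that the death was not cardiovascular.

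This has two consequences. A fatal case that is neither infarction nor stroke drops out of the MACE table, although the board did not exclude a cardiovascular cause. A fatal case adjudicated as infarction or stroke stays in the table but is called non-fatal. The second sits badly with section 5.4.2.2.7, where an AE is fatal if its reported outcome is fatal: one case could be a fatal SAE in one table and a non-fatal infarction in another.

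What is at stake is how a long-term safety report describes a few serious events. Long-term safety is the first stated objective (section 1.1.1), and bradyarrhythmia after the first dose is on the AESI list in section 5.4.2.2.10. A reader looking for possible cardiovascular deaths would turn first to the only adjudicated cardiovascular table.

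**Working it through.** The plan gives no figure to reproduce, so the check applies its four rules to every combination of the two adjudication questions.

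**Inputs**, all from section 5.4.2.2.11: three event types (infarction, stroke, other AE); four fatality states (not fatal, or a death of cardiovascular, non-cardiovascular or undetermined cause); the four category rules set out above.

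**Result for the 12 combinations:**

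| Fatality state | Infarction | Stroke | Other AE |
|---|---|---|---|
| Not fatal | non-fatal MI | non-fatal stroke | no MACE |
| Death, cardiovascular | CV death | CV death | CV death |
| Death, non-cardiovascular | non-fatal MI | non-fatal stroke | no MACE |
| Death, undetermined | non-fatal MI | non-fatal stroke | no MACE |

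Every combination receives exactly one category, so the rules are complete and do not overlap. The last two rows are identical, so the undetermined verdict has no effect of its own. Of its three combinations, one (other AE) leaves MACE. The other two are counted as MACE under a label that says the subject did not die of the event, which the board has not established.

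**What other outputs show about such a death:**

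- Section 5.4.2.3.2 tabulates deaths during the extension study by reported primary cause, and lists all deaths. The cause comes from the Death eCRF (section 5.4.2.2.8), not from adjudication.
- Section 5.4.2.3.1 counts any fatal SAE in the TEAE overview. Section 5.4.2.3.3 lists fatal SAEs, and tabulates treatment-emergent ones only if there are more than 5.
- Section 5.4.2.3.5 counts fatal events within each AESI category, independently of adjudication, if the preferred term qualifies. None of the preferred terms that Table 10 names for bradyarrhythmia is a death term; the content of the accompanying SMQ is not shown.

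The death itself is reported, but none of these outputs shows that the board left its cause open.

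**Scale.** The SAP does not say how many such cases exist. Section 3 gives 877 enrolled subjects, so one other-AE case moved into a MACE total adds 1/877 = 0.114 percentage points. If there were 1 to 5 such cases (an assumption), the addition would be 0.11 to 5/877 = 0.57 percentage points. With none, it is zero. The 877 serves only for scale: the Extension table uses treated subjects, and percentages within a core treatment group have a smaller denominator.

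**The case against.** The strongest defence is that the rule is explicit and complete, and that restricting cardiovascular death to deaths adjudicated as such is a legitimate convention. The study is open-label and non-comparative (section 1.2), all analyses are exploratory (section 2), and no test depends on this table. The deaths are visible elsewhere. All of this stands. It limits the weight of the point and argues against putting undetermined deaths into the headline MACE figure. It does not justify calling a case non-fatal when the subject died and the cause is open, or leaving a recorded board verdict out of the table.

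Several stronger readings are tempting but not supported:

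- *All deaths of undetermined cause fall out of MACE.* Only those with an event type of other AE do.
- *The SAP otherwise always resolves unknown safety information against the drug.* It often does: for seriousness, "in case information on seriousness is missing, the AE is conservatively considered to be serious", and sections 5.4.2.2.12 and 5.4.2.2.13 do the same for severity and relationship. But section 6.13.3.1 keeps AEs with missing or partial onset dates out of the Day 1 summaries, and section 5.4.2.1 treats AEs ongoing from the core study as not treatment-emergent in the extension, without imputing their dates. Those conservative rules also concern missing fields, whereas undetermined is a recorded verdict.
- *An unwitnessed arrhythmic death would typically be adjudicated as undetermined.* The SAP shows neither the board's criteria nor the preferred-term list that sends cases to it. A board that classed such deaths as cardiovascular would be equally consistent with the text.
- *MACE is understated by 11% to 50%.* That follows from assuming 3 to 8 counted MACE and 1 to 3 undetermined deaths: 1/(8+1) = 11% and 3/(3+3) = 50%. Neither count is in the document. The formula also requires every such death to be an other-AE case and truly cardiovascular, and leaves out the possibility of no such deaths.

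**Conclusion.** The point holds as a gap in classification and display. Section 5.4.2.2.11 gives the undetermined verdict no analysis category, and section 5.4.2.3.6 does not make up for it. The adjudicated table can therefore understate possible cardiovascular deaths and can label a fatal infarction or stroke case as non-fatal.

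This follows from the text alone and needs no assumption about event numbers. Its practical size does: it is nil if no death was adjudicated as undetermined, and about 0.11 percentage points of the 877 enrolled for each other-AE case. For infarction and stroke cases the MACE total is unaffected; only the label is wrong.

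A reader might infer that deaths are hidden or that the MACE total is known to be biased. The documents support neither. This is an inexpensive improvement to a descriptive safety table and does not challenge the study's conclusions.

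**What to change.** In section 5.4.2.2.11:

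- Add a category, death of undetermined cause, for fatal cases adjudicated as other AE with undetermined cause. Limit no MACE to the remaining other-AE cases.
- Keep infarction and stroke cases with undetermined cause of death within MACE, but label them for what they are, for example myocardial infarction (or stroke) with death of undetermined cause.

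In section 5.4.2.3.6:

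- Show the new category as its own row, and include these cases in the listing.
- Report any MACE without the new category and, as a sensitivity count, with it. Infarction and stroke cases with undetermined cause of death belong in both totals; moving them into the new category would remove events from the first total that the present rule counts.

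No new data are needed, because the board already records the cause of death. The cost is a few lines of SAP text, one or two table rows, and a sensitivity count that may look slightly less favourable.

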5.4.2.2.12. Intensity of adverse events

AE intensity is entered into the database as 'Mild', 'Moderate', or 'Severe'. For AEs reported more than once for a subject, only the worst outcome is considered. AEs with missing severity assessment are imputed to be of 'severe' intensity.

5.4.2.2.13. Relationship of adverse events

Relationship to study treatment is entered into the database as 'related' or 'not related'. For AEs reported more than once for a subject, only the worst relationship is considered. AEs with missing relationship are considered to be related.

5.4.2.3. Analysis of safety variables

If not otherwise stated, only safety data considered treatment-emergent (up to 15 days after the last treatment administration) in the respective Analysis Period will be included in tables and figures. Additionally, non-treatment-emergent data at Core Day-15 follow-up, Core Day-30 follow-up and extension EOS visits may also be included in certain tables and figures. All safety data will be included in listings, with flags for safety data considered to be treatment-emergent to a specific Analysis Period.

Generally, safety data are presented as follows:

Safety data collected in the extension study will be analyzed based on the **Extension Analysis Period** using the EXTS and will be summarized for all subjects overall and split by core study treatment group. The analysis of change from baseline for safety endpoints assessed by visit will use the extension baseline as reference.

Furthermore, the long-term safety of ponesimod 20 mg and the changes in safety for teriflunomide 14 mg subjects switching to ponesimod 20 mg will be assessed by summarizing all data in the **Combined Analysis Period** using the SAF. Cumulative data such as AEs and SAEs will only be summarized for subjects initially treated with ponesimod 20 mg in the core study. Safety endpoints assessed by visit will be summarized by core study treatment group. Analysis of change from baseline for safety endpoints assessed by visit will use the core baseline as reference, unless otherwise specified.

5.4.2.3.1. Adverse events

Unless otherwise specified, all the AE summaries described below are produced for the Combined Analysis Period (only for subjects included in the SAF who were initially treated with ponesimod 20 mg in the core study) and for the Extension Analysis Period by core study treatment and overall, using the EXTS.

An overview of TEAEs is presented, per study treatment group, as the number and percentage of subjects having any AE, any severe AE, any drug-related AE, any AE leading to study drug discontinuation, any SAE, any drug-related SAE, or any fatal SAE. Similarly, an overview of TEAEs per 100 subject-years is also presented.

The following summary tables will be created to present the frequency and percentage of subjects with any AE, an AE in each primary SOC, and each individual AE (preferred term). SOCs are sorted by descending order of frequency in the ponesimod arm. If the frequencies of SOCs are the same, alphabetical order is used. The same rule applies for preferred terms within SOC:

- All AEs;
- TEAEs;
- TEAEs per 100 subject-years; TEAEs with onset on Day 1 of a re-initiation (all re-initiations summarized together, for subjects with at least one re-initiation), Extension Analysis Period only:
- TEAEs leading to permanent discontinuation of study treatment;
- TEAEs considered to be related to study drug;
- Severe TEAEs;
- Post-treatment AEs (subjects that entered the period between EOT date + 16 and EOS), Extension Analysis Period only.

The following summary tables will also be produced, presenting the frequency and percentage of subjects with any AE, and each individual AE (preferred term) by descending frequency:

CONFIDENTIAL – FOIA Exemptions Apply in U.S.

- TEAEs;
- TEAEs per 100 subject-years;
- TEAEs leading to permanent discontinuation of study treatment;

• TEAEs reported in \geq 5% of subjects in any group (after rounding into the 1st decimal in percentage, e.g. an event occurring in 4.955% of subjects will be rounded to be 5.0% and therefore be included in this summary table).

The following summary tables will also be produced, presenting the frequency and percentage of subjects with any AE, and each individual AE (preferred term) by maximum intensity:

• TEAEs.

AEs (preferred terms) reported more than once in a subject during the period summarized are counted once in frequency tables. Percentages are based on the SAF (ponesimod subjects) or on the EXTS as applicable.

5.4.2.3.2. Deaths

The number and percentage of subjects who died during the extension study are summarized per core study treatment group, including the reported primary cause of death.

A separate listing including all deaths will be provided; treatment-emergent deaths will be flagged as such in that listing.

5.4.2.3.3. Serious adverse events (SAEs)

SAEs are summarized by SOC and preferred term. The following summaries are presented:

- Treatment-emergent SAEs;
- Treatment-emergent SAEs per 100 subject-years;
- Treatment-emergent SAEs with onset on Day 1 of a re-initiation (for subjects with at least one re-initiation), Extension Analysis Period only;
- Treatment-emergent SAEs leading to permanent discontinuation of study treatment
- Treatment emergent SAEs with fatal outcome; (this will be tabulated only if there are more than 5 SAE-caused fatal events)

In addition, the following summary tables will also be produced, presenting the frequency and percentage of subjects with any SAE, and each individual SAE (preferred term) by descending frequency:

- Treatment-emergent SAEs;
- Treatment-emergent SAEs leading to premature discontinuation of study drug, Extension Analysis Period only.

SAEs, SAEs leading to hospitalization, and fatal SAEs will be presented in dedicated listings.

5.4.2.3.4. Treatment-emergent adverse events leading to study treatment discontinuation

AEs and SAEs leading to premature discontinuation of study drug are summarized by SOC and preferred term as listed above.

A listing for AEs leading to premature discontinuation of study drug will be presented.

5.4.2.3.5. Adverse events of special interest (AESIs)

For each of the AESI categories described in Section 5.4.2.2, the number and percentage of subjects with each AESI is summarized by core treatment group and preferred term for treatment-emergent AESIs. In addition, the number and percentage of subjects having any event of that category, having any serious event, any fatal event or any event leading to premature discontinuation of study drug is presented. Similarly, treatment-emergent AESIs per 100 subject-years are summarized per AESI category.

AESI are presented in dedicated listings (one for each AESI category).

5.4.2.3.6. Major adverse cardiovascular events (MACE)

A summary table will be produced for the Combined Analysis Period on the FAS and for the Extension Analysis Period on the EXTS presenting the frequency and percentage of subjects with any treatment-emergent MACE and having an event of the MACE subcategories (cardiovascular death, non-fatal myocardial infarction, non-fatal stroke) per core treatment group.

MACE are also presented in a dedicated listing.

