4.1.3. Full analysis set (FAS)

Following the intention-to-treat (ITT) principle, the full analysis set (FAS) includes all subjects randomized in the core study. Subjects will be evaluated according to the treatment they have been randomized to in the core study, which may be different from the treatment they have received.

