4.1.4. Safety set (SAF)

The safety set (SAF) includes all subjects who received at least one administration of core study treatment. Subjects will be analyzed according to the treatment they received during the core study.

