4.2. Usage of the analysis sets

The EXTS will be used for efficacy and safety analyses of the Extension Analysis Period. The FAS and EXTS will be used for efficacy analyses of the Combined Analysis Period. The SAF will be used for the safety analysis of the Combined Analysis Period in an as-treated approach. The DLCO SAF and the DLCO EXTS will be used for analyses of the DL_{CO} sub-study endpoints on the Combined Analysis Period and in the Extension Analysis Period respectively. Table 6 below provides an overview of analysis set in use for efficacy and safety endpoints. More details are depicted in the respective section.

Table 6: Use of analysis set

Endpoint category	Endpoint	Combine period 1			Extensi	Extension period	
category	gory	FAS	EXTS	SAF	DLCO SAF	EXTS	DLCO EXTS
Efficacy	ARR	Y	Y			Y	
ř	Time from core study randomization to first confirmed relapse	Y	Y				
	Duration of relapse		Y			Y	
	Absence of relapse		Y			Y	
	Time from core baseline to 12-week CDA	Y	Y				
	Time from core baseline to 24-week CDA	Y	Y				
	Change from baseline in EDSS		Y			Y	
	Gd+ T1 lesions by visit		Y			Y	
	New or enlarging T2 lesions		Y			Y	
	by visit						
	Cumulative new or enlarging T2		Y			Y	
	CUAL by visit		Y			Y	
	Cumulative CUAL	Y	Y			Y	
	Total Volume of T1 hypointense lesions and the change from baseline		Y			Y	
	Total volume of T2 lesions and the change from baseline		Y			Y	
	Proportion of T1 Gd+ lesions at baseline evolving to PBHs (persistent black holes) at all assessments		Y			Y	
	Percentage change in Brain volume from baseline	Y	Y			Y	
	NEDA status at EOS according to NEDA 3		Y				
	NEDA status at EOS according to NEDA 4		Y				
	Change from baseline in MSFC Z-score		Y			Y	
	Change from baseline in the SDMT score		Y			Y	
	Change from baseline in SF-36v2 TM Health Survey		Y			Y	

Table 6: Use of analysis set

Endpoint	Endpoint	Combine period				Extension period	
category		FAS	EXTS	SAF	DLCO SAF	EXTS	DLCO EXTS
	domain and component scores						
Safety	Exposure			Y		Y	
	Adverse Event			Y		Y	
	Laboratory test and the associated abnormal findings			Y		Y	
	Vital signs and the associated abnormal findings			Y		Y	
	ECG and the abnormal findings			Y		Y	
	Pulmonary safety and the associated abnormal findings (except lung diffusing capacity)			Y		Y	
	Diffusing capacity				Y		Y
	eC-SSRS			Y			
Demographic	Demographic		Y				
Disposition	Disposition	Y	Y				

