5.4.2. Adverse Events

5.4.2.1. General consideration in adverse events

An AE is any event reported by the investigator on the Adverse Event eCRF.

AEs that started in the core study and were still ongoing on Day 1 of the extension study are reported in the 'Ongoing Adverse Events from AC-058B301' extension eCRF form. If the event worsened in intensity/seriousness after start of study treatment in the extension study, such an event was reported in the usual Adverse Event eCRF Form.

All AEs are coded using the MedDRA dictionary (version 26.0).

For the summaries on the Combined Analysis Period, AEs from core and extension study (specifically AEs included in the extension eCRF as 'ongoing' from the core study and the original AEs included in the core eCRF) will be merged using a dedicated ID linking variable included in the related SDTM datasets. The following rules will be used by merging the SDTM datasets:

- If information regarding the seriousness of an ongoing AE is inconsistent between the two databases, the AE is conservatively considered to be serious;
- The outcome as entered in extension study will be used for the analysis;
- If the action taken for an ongoing AE is given as temporarily interrupted in the core study database, and the action taken is missing, none, not applicable, or unknown in the extension study database, then the value from the core will be retained. For all the other cases the action taken as entered in extension study will be used for the analysis;
- If an event entered on the form "Ongoing adverse events from AC-058B301" eCRF page in the extension, this AE will not be considered as treatment-emergent with respect to the Extension Analysis Period, and no dates or other variables will be imputed if missing or partial. Such events will appear in listings only.

For the Combined Analysis Period, cumulative data such as AEs and SAEs will only be summarized for subjects initially treated with ponesimod 20 mg in the core study.

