Furthermore, **self-injurious behavior without suicidal intent** is also an eC-SSRS outcome (although not suicide-related) and has a binary response (yes/no), this will be assigned as score 11 and to be summarized for subjects with these events.

The initial assessment has a lifetime and a recent history assessment. The recent history covers the last 1 month for suicidal ideation, and the last 3 months for suicidal behavior. Recent history questionnaire questions are only assessed for outcome categories with corresponding lifetime outcome question answered as yes. If the lifetime assessment for an outcome category is 'No', also the corresponding recent history outcome is considered 'No' for analysis. The "lifetime and a recent history assessment" is performed twice during the course of the study, respectively at core study baseline and at extension visit 7 – week 48.

Scoring: Scores are created at each assessment as follows:

- **Suicidal Ideation Score**: The maximum suicidal ideation category (1–5 on the eC-SSRS) present at the assessment. Assign a score of 0 if no ideation is present.
- **Suicidal Behavior Score:** The maximum suicidal behavior category (6–10 on the eC-SSRS) present at the assessment. Assign a score of 0 if no behavior is present.

For each assessment timepoint, a subject with multiple reported outcomes for suicidal ideation and suicidal behavior will be summarized under the worst reported outcome (i.e., max[1-5] and max[6-10], respectively).

Throughout all post-baseline assessments, a subject can have multiple suicidal ideation or suicidal behaviors, the worst reported outcome will be considered as the post-baseline outcome.

The following definitions will be used:

- Suicidal ideation: A "yes" answer to any one of the five suicidal ideation questions (Categories 1-5) on the eC-SSRS. Taken from the 'Reported most severe ideation level'.
- **Suicidal behavior**: A "yes" answer to any one of the five suicidal behavior questions (Categories 6-10) on the eC-SSRS.
- Suicidal ideation or suicidal behavior
- Serious suicidal ideation (score \geq 4) or suicidal behavior

The definitions above will be defined at any time in the period from study treatment start up to Extension EOT + 15 days*, for pre-treatment lifetime, and for pre-treatment recent history.

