Suicidal Ideation and Suicidal Behavior score categories: Shifts from baseline (worst outcome from pre-treatment recent history) to the worst outcome up to Extension EOT + 15 days (inclusive) will be derived using the following categories: No ideation (score 0), non-serious suicidal ideation (score 1-3), serious suicidal ideation (score 4-5), suicidal behavior (score 5-10).

*Only post-baseline assessments after study treatment start date from a 'since last call' questionnaires and the "Recently" questionnaire assessed at B303 extension week 48 (visit 7) are considered for the analysis.

Baseline is defined as last available recent history result (maximum score) up to study treatment start date at core study, i.e., pre-treatment recent history result at core baseline. This is taken from the answers to the "Recently" category questionnaires at core study baseline. If the lifetime assessment at core study baseline for an outcome category is 'No', also the corresponding recent

history outcome is considered 'No' for analysis. The core study baseline has already been derived and captured in B301 ADaM dataset and can be used directly.

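### Combined-period MACE are tabulated on the randomized set by core arm, against the SAP's own safety-set rules, and the eC-SSRS shift categories overlap at score 5

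*SAP*

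**What the plan says.** **MACE.** Section 5.4.2.3.6 states: "A summary table will be produced for the Combined Analysis Period on the FAS and for the Extension Analysis Period on the EXTS". The table counts subjects with treatment-emergent MACE and its subcategories "per core treatment group". Under section 4.1.3, "the full analysis set (FAS) includes all subjects randomized in the core study", evaluated by randomized treatment. Under section 4.1.4, "The safety set (SAF) includes all subjects who received at least one administration of core study treatment", analyzed by treatment received.

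Section 4.2 fixes the set for this period: "The SAF will be used for the safety analysis of the Combined Analysis Period in an as-treated approach". Table 6 marks adverse events under the SAF and not under the FAS. For the same period, section 5.4.2.1 adds this limit: "cumulative data such as AEs and SAEs will only be summarized for subjects initially treated with ponesimod 20 mg in the core study". The Table 2 footnote and section 5.1.5.2 carry the same restriction. Section 5.1.2 shows combined-period adverse events and treatment-emergent incidence only for the ponesimod/ponesimod group on the SAF.

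**eC-SSRS.** Among its shift categories, section 5.4.3.9.1 lists "serious suicidal ideation (score 4-5), suicidal behavior (score 5-10"). Earlier in the same section the behavior score is defined as "The maximum suicidal behavior category (6–10 on the eC-SSRS) present at the assessment", and Table 8 places category 5 under ideation. Section 5.4.3.9.2 then names only three shift categories: no ideation, non-serious ideation and serious ideation.

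**The concern.** MACE and suicidality are rare outcomes that are read closely, so a few misplaced subjects alter the table.

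For MACE, the section names a different population from the one the SAP fixes elsewhere for combined-period safety, and it does not repeat the restriction to core-ponesimod subjects. A programmer who follows it literally produces a column for subjects who took teriflunomide in the core study. That column would mix time on two drugs and group subjects by randomized instead of received treatment.

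For the eC-SSRS, one score belongs to two categories that ought to be exclusive. The analysis section also gives no row to the most serious category, so a subject whose worst score is 5 could be shown as having suicidal behavior, and a subject with true behavior has no named place in the shift table.

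**Working it through.** The plan gives no figure to reproduce here. The check sets its rules side by side and adds some simple arithmetic.

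**1. Population for combined-period MACE**

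| Point | General rule | Section 5.4.2.3.6 |
|---|---|---|
| Analysis set | SAF (4.2, Table 6, 5.4) | FAS |
| Grouping | Treatment received (4.1.4, 5.1.5.2) | Randomized treatment, through the FAS (4.1.3) |
| Arms shown | Core ponesimod only (Table 2 footnote, 5.1.2, 5.4.2.1) | Per core treatment group, no restriction stated |

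MACE fall under the adverse-event rules because section 5.4.2.2.11 takes their onset date and treatment-emergent status from the linked adverse event. Sections 5.4.1.2.1 and 5.4.1.2.2 (exposure and compliance) also name the FAS, but at once limit it to SAF subjects first treated with ponesimod. The MACE section has no such limit.

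**2. Treatment emergence in the teriflunomide/ponesimod column**

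Section 5.4.2.2.2 anchors combined-period emergence to the first ponesimod dose in the core study. A subject treated with teriflunomide had no such dose. Sections 5.1.1.2 and 5.1.6 instead start from study treatment in general. Under those sections teriflunomide-phase events count; under 5.4.2.2.2 their status is undefined.

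**3. Subjects without extension data**

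Section 3 gives 1133 randomized and 877 enrolled in the extension.

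- Not enrolled: 1133 − 877 = 256, and 256/1133 = 22.6%, across both arms. The split by arm is not given.
- Section 5.1.1.2 keeps these subjects in the combined period. Any of them treated with teriflunomide would contribute only teriflunomide time to a column labeled as teriflunomide followed by ponesimod.

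**4. Denominator effect alone**

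The SAF size is not stated. Assume 0 to 20 of the 1133 were never treated, and take 10 subjects with an event for illustration.

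- FAS: 10/1133 = 0.883%
- SAF, 0 untreated: 10/1133 = 0.883%
- SAF, 20 untreated: 10/1113 = 0.898%

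The difference is under 0.02 percentage points. What matters is who is counted and under which drug.

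**5. eC-SSRS score ranges**

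- Shift categories as written: {4, 5} ∩ {5, …, 10} = {5}.
- Using the behavior definition in the same section: {4, 5} ∩ {6, …, 10} = empty.

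The behavior score itself can only be 0 or 6 to 10. The overlap therefore takes effect when a single maximum over ideation and behavior is sorted into the four categories. Section 5.4.3.9.2 refers to the maximum score at baseline and to the maximum score as the worst outcome, which invites that use.

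**The case against.** **The MACE section may be a deliberate exception.** Sections 5.1.2, 5.4, 5.4.2.3 and 5.4.2.3.1 allow for exceptions stated elsewhere. But section 4.2, section 5.4.2.1 and the Table 2 footnote state their rules without one, and Appendix 2 gives no reason for treating MACE differently.

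**The mixed column may never be produced.** The grouping phrase ends a sentence that covers both periods, and section 5.4.2.3.5 uses nearly the same phrase for events of special interest. If the core-ponesimod restriction governs MACE too, there is no combined teriflunomide column, and the fault is an omitted qualifier. That is a fair reading, and probably the intended one. It still requires a correction, because the literal text says otherwise.

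**Stronger readings that the SAP does not support:**
- A reader might infer that MACE is the only combined-period table outside the restriction. It is not. The eDISH plot in 5.4.3.1.2, the lymphocyte incidence in 5.5.3 and the worst eC-SSRS outcome in 5.4.3.9.2 carry no core-ponesimod limit.
- A reader might suppose that the restriction exists because teriflunomide-phase events cannot be attributed to ponesimod. Section 5.1.5.2 gives another reason: a long-term assessment of up to 6 years.
- A reader might take 108/(108 + 240) = 31% as the largest share of teriflunomide time in the switch column. It is the planned share for someone who completes both periods. Early stoppers have more, and subjects who never entered the extension have 100%.
- A reader might fear that score 11 (self-injury without suicidal intent) could mask a behavior score. Section 5.4.3.9.1 takes the worst outcomes within 1-5 and within 6-10, so 11 lies outside both.

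**The eC-SSRS slip is narrow.** The incidence definitions are right, section 5.4.3.9.1 names all four shift categories, and section 5.4.3.9.2 also tabulates behavior overall and by category and lists positive visits. This stands: behavior is not lost from the report, only from the shift categories named in 5.4.3.9.2.

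**Conclusion.** The SAP is wrong as written in two places, and both are inexpensive to correct.

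The combined-period MACE table contradicts the SAP's rules on analysis set, grouping and arms. For the teriflunomide arm it also has no consistent definition of treatment emergence. How many events are affected cannot be derived from the document. The choice of denominator alone moves the percentage by less than 0.02 points, assuming 10 events and at most 20 untreated subjects. The consequence that matters is a column pooling two drugs, and it follows only if the section is read literally.

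The eC-SSRS shift categories overlap at exactly one score, most likely through a typing error, and the analysis section leaves out the behavior category. Subjects whose worst score is 5 are affected only if one pooled maximum is used.

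All analyses in this study are descriptive and MACE are also listed by subject, so this concerns the accuracy of two safety tables and no hypothesis test.

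**What to change.** - **Section 5.4.2.3.6:** put the combined-period MACE table on the SAF, restricted to subjects initially treated with ponesimod 20 mg in the core study. This also makes the emergence rule in 5.4.2.2.2 usable. The Extension Analysis Period table on the EXTS by core group stays as it is and already shows the subjects who switched.
- **Section 5.4.3.9.1:** change the score range for suicidal behavior in the shift categories from 5-10 to 6-10.
- **Section 5.4.3.9.2:** add suicidal behavior as the fourth shift category, so that the list agrees with 5.4.3.9.1.

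The cost is a few words of SAP text and edits to two table shells. No new data or derivations are needed.
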